#### **11.2.1 Treatment-Emergent Adverse Events**

All adverse events occurring between start of treatment and end of the residual effect period (REP) will be considered 'treatment emergent.' The REP is defined as 20 weeks (140 days) after the last trial medication application and will include adverse events reported through EOS visit. Adverse events that start before first drug intake and deteriorate under treatment will also be considered as 'treatment-emergent.'

Events where the onset date is the same as the study drug start date are assumed to be treatment emergent, unless the study drug start time and the adverse event start time are

collected and the adverse event start time is prior to the study drug start time. If an incomplete onset date is collected for an adverse event, the event will be assumed to be treatment-emergent unless there is other evidence that confirms that the event is not treatment-emergent (e.g., the event end date is prior to the study drug start date).

Adverse events that occur outside of 140 days from last dose in Study 1311.5 but before first dose in Study M16-244 will not be considered treatment emergent.

The number and percent of subjects experiencing treatment-emergent TEAEs will be tabulated using the Medical Dictionary for Drug Regulatory Activities (MedDRA®) version 20.0 by system organ class (SOC) and preferred term (PT).

**Summary tables of TEAEs will be presented as follows:**

**1. Overview of TEAEs**

The number and percentage of subjects experiencing TEAEs will be summarized for the following adverse event categories:

- Any TEAEs
- Any severe TEAEs
- Any serious TEAEs
- Any related TEAEs
- Any TEAEs leading to discontinuation of study drug
- Any TEAEs leading to death
- Any deaths
- Any TEAEs of area of safety interest

**2. Adverse Events by System Organ Class and Preferred Term**

The number and percentage of subjects experiencing TEAEs will be tabulated according to the primary MedDRA SOC and PT for each prior and current treatment group. Subjects reporting more than one adverse event for a given MedDRA PT

will be counted only once for that term (most severe incident for the severity tables and most related incident for the relationship tables). Subjects reporting more than one type of adverse event within a SOC will be counted only once for that SOC. Subjects reporting more than one type of adverse event will be counted only once in the overall total.

The system organ classes will be presented in alphabetical order and the preferred terms will be presented in alphabetical order within each system organ class.

### **3. Adverse Events by Maximum Severity/Toxicity**

The severity grading of AEs follows Rheumatology Common Toxicity Criteria (RCTC).

- Grade 1 – mild
- Grade 2 – moderate
- Grade 3 – severe
- Grade 4 – life threatening

The TEAEs will also be summarized by maximum severity. If a subject has an adverse event with unknown severity, then the subject will be counted in the severity category of "unknown," even if the subject has another occurrence of the same event with a severity/toxicity present. The only exception is if the subject has another occurrence of the same adverse event with the most extreme severity (e.g., "Life threatening"). In this case, the subject will be counted under the "Life threatening" category.

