8.1.6.2 Analysis of Adverse Events**8.1.6.2.1 Treatment-Emergent Adverse Events**

AEs will be coded using MedDRA. A TEAE is defined as an AE that began or worsened in severity after initiation of study drug. AEs starting more than 140 days following the last dose of study drug will not be included in summaries of TEAEs.

As a general safety summary, the number and percentage of subjects experiencing TEAEs will be summarized for each treatment group for the following AE categories:

- All TEAEs;
- All severe TEAEs;
- All reasonably possibly related TEAEs;
- All SAEs;
- Discontinuations due to TEAEs;
- All TEAEs of special interest
- Death.

Additional TEAEs may be considered for tabulation/summary based on recommendations from Clinical and Safety as deemed appropriate.

TEAEs will be summarized and presented by SOCs and PTs using MedDRA. The SOCs will be presented in alphabetical order, and the

PTs will be presented in alphabetical order within each SOC.

TEAE will also be summarized by maximum severity and by maximum relationship.

The intensity grading of AEs will be performed according to Rheumatology Common Toxicity Criteria (RCTC) Version 2.0 developed by OMERACT.¹¹ Intensity options are:

Grade 1 mild

Grade 2 moderate

Grade 3 severe

Grade 4 life-threatening

The TEAEs of special interest currently include hepatic injury.

Listing of all SAEs, AEs leading to death, and TEAEs leading to study drug discontinuation and TEAE of special interest will be generated.

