### **4. Adverse Events by Maximum Relationship**

Adverse events will be summarized by maximum relationship to study drug, as assessed by the investigator. Relationship of an AE to study drug is assessed by the investigator and collected in the CRF as 'Yes' or 'No.' If a subject has an adverse event with unknown relationship, the subject will be counted in the relationship category of "unknown," even if the subject has another occurrence of the same event with a relationship of "No." If the subject has another occurrence of the same

adverse event with a relationship assessment of "Yes," the subject will be counted under the "yes" category.

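### In the maximum-severity table, an ungraded occurrence overrides a known Grade 3 occurrence of the same event and moves the subject from the severe row to the unknown row

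*SAP*

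**What the plan says.** Protocol 8.1.6.2.1 asks for the table without saying how to treat an ungraded event: "TEAE will also be summarized by maximum severity and by maximum relationship".

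SAP 11.2.1, item 3, prints a four-step scale that ends with "Grade 3 – severe" and "Grade 4 – life threatening". It then places a subject who has any ungraded occurrence of an event in the unknown category, "even if the subject has another occurrence of the same event with a severity/toxicity present". It allows one way out: "The only exception is if the subject has another occurrence of the same adverse event with the most extreme severity". The example given, and the category to which such a subject is sent, is life threatening.

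SAP 11.2.1, item 2, sets the counting rule for repeated events under one preferred term. The subject "will be counted only once for that term (most severe incident for the severity tables and most related incident for the relationship tables".

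SAP 11.2.1, item 4, has a similar rule for relationship. Unknown prevails "even if the subject has another occurrence of the same event with a relationship of" No, but a Yes prevails over unknown.

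**The concern.** The primary objective is safety and tolerability, and the severity table is one of its main displays. For a subject with a Grade 3 and an ungraded occurrence of the same event, the maximum is known to be at least severe. Item 3 sets that knowledge aside. Compared with counting the highest known grade, the rule can only take subjects out of the Grade 1, 2 and 3 rows and never adds any, so the severe row can only be too low.

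The rule also does not fit item 2. Two programmers, one working from each item, would build different tables from the same data. In addition, the overview in item 1 has a row for severe treatment-emergent events with no such rule stated. The same subject could be severe in the overview and unknown in the severity table.

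**Working it through.** The documents give no figure to reproduce here. The check has two parts: applying the stated rules to every case, and sizing the effect on assumed inputs.

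**1. Rules applied to every case.** Inputs: the scale (Grades 1 to 4) and the unknown rule from item 3, and the worst-incident rule from item 2, read as the highest known grade. With two occurrences of one preferred term in one subject, one of them ungraded:

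| Occurrences | Item 3 | Highest known grade |
|---|---|---|
| Grade 1, ungraded | unknown | Grade 1 |
| Grade 2, ungraded | unknown | Grade 2 |
| Grade 3, ungraded | unknown | Grade 3 |
| Grade 4, ungraded | Grade 4 | Grade 4 |

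The rules differ in three of the four cases. With three occurrences there are 14 mixtures of graded and ungraded: 10 with one ungraded and 4 with two. Five of the 14 contain a Grade 4 and keep it. The other 9 go to unknown, and in 4 of those 9 the highest known grade is 3: {1, 3, ungraded}, {2, 3, ungraded}, {3, 3, ungraded} and {3, ungraded, ungraded}.

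**2. Comparison with the relationship rule.** In items 3 and 4 alike, the top category beats unknown and unknown beats everything below the top. Relationship has two levels, so the top category is the whole adverse category and is fully protected. Severity has four levels, so protecting only the top leaves severe exposed.

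**3. Size.** The SAP expects up to 180 subjects. Two quantities are assumed: s, the number of subjects whose worst known grade is 3, and q, the chance that such a subject also has an ungraded occurrence of the same term. Each subject is taken to have one relevant term, independently of the others.

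- Expected number moved = s × q
- Chance that at least one moves = 1 − (1 − q)^s

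| s (share of 180) | q = 1% | q = 5% | q = 10% |
|---|---|---|---|
| 5 (2.8%) | 0.05; 4.9% | 0.25; 22.6% | 0.5; 41.0% |
| 10 (5.6%) | 0.1; 9.6% | 0.5; 40.1% | 1.0; 65.1% |
| 18 (10.0%) | 0.18; 16.5% | 0.9; 60.3% | 1.8; 85.0% |

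Each cell gives the expected number moved, then the chance that at least one moves. For s = 10 and q = 10%, the expected Grade 3 row falls from 10/180 = 5.6% to 9/180 = 5.0%.

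**The case against.** The best defence is that item 3 is coherent. When one occurrence is ungraded, the true maximum is certain only if another occurrence is already at the top of the scale. Otherwise it is indeterminate, and unknown says so. The protocol is silent on ungraded events, so the rule does not break it. Counting the highest known grade has a bias of its own, because a subject with a Grade 1 and an ungraded occurrence would appear as mild.

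Much of this stands, but it does not rescue the treatment of Grade 3. There the only open question is whether the maximum is 3 or 4; that it is at least severe is settled. SAP 10.7.1 handles missing ACR components this way: it gives an answer whenever the observed components decide the matter, and sets the response to missing only when they do not. A footnote can carry the uncertainty that remains.

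Ungraded events should also be uncommon. Protocol 6.1 has the investigator record severity for each event, Protocol 6.1.2 offers four grades and no unknown option, and Protocol 10.2 has the case report forms reviewed for completeness. This limits the size of the problem.

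Three stronger readings are tempting, and the documents do not support them:

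- **Severe events vanish from the severity table or from the report.** The subject stays in the table in a visible unknown row. The overview row, the summaries of moderate or severe events by grouped term (SAP 11.2.1, item 7), and the tables and listings of serious events and of events leading to discontinuation (items 6 and 11) state no such rule.
- **The relationship rule runs in the opposite direction.** It has the same structure, and only the number of levels differs.
- **The under-count is material.** Nothing in the documents gives a rate of ungraded events.

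**Conclusion.** The point holds as a defect in a counting rule. Read literally, item 3 moves a subject with a known Grade 3 occurrence to unknown, because Grade 3 is not the most extreme severity on the printed scale. The 'e.g.' in the exception does not change that. Items 2 and 3 conflict and must be reconciled however often the case arises. Disagreement with the overview row is possible but not certain, because the SAP does not say how that row treats ungraded events.

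The numerical effect is probably small. It needs a Grade 3 and an ungraded occurrence of the same event in one subject. On the central assumption of 10 such Grade 3 subjects among 180, it comes to 0.1 to 1.0 subjects for q between 1% and 10%, and across the whole grid to between 0.05 and 1.8. The values of s and q are illustrations, not estimates. The study is single-arm and descriptive, and no decision rule rests on this table. The case for changing the rule is that it discards a known severe grade and that correcting it costs almost nothing.

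**What to change.** Rewrite item 3 to agree with item 2:

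- Count each subject at the highest known grade for the event.
- Use unknown only when none of the subject's occurrences of that event has a grade.
- Footnote, for each row, the number of subjects who also have an ungraded occurrence of the same event.

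If the sponsor prefers to keep unknown for low grades, the minimum change is to let Grade 3 as well as Grade 4 override it. The SAP should also state that the overview row for severe events treats ungraded occurrences in the same way.

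The cost is one sentence in the SAP, a footnote and a minor programming change, with no new data. The small downside is that a subject with a low grade and an ungraded occurrence is shown at the low grade, which the footnote discloses.

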### **4. Adverse Events by Maximum Relationship**

Adverse events will be summarized by maximum relationship to study drug, as assessed by the investigator. Relationship of an AE to study drug is assessed by the investigator and collected in the CRF as 'Yes' or 'No.' If a subject has an adverse event with unknown relationship, the subject will be counted in the relationship category of "unknown," even if the subject has another occurrence of the same event with a relationship of "No." If the subject has another occurrence of the same

adverse event with a relationship assessment of "Yes," the subject will be counted under the "yes" category.

#### 5. **TEAEs by Preferred Term in Descending Frequency**

TEAEs, SAEs, and TEAEs leading to discontinuation of study drug will be summarized by prior and current treatment group in decreasing order of frequency of MedDRA PT in the total risankizumab doses, including AEs occurring after the first dose in Study M16-244 for subjects who received Placebo in Study 1311.5, as well as the highest dose arm from Study 1311.5. The most frequent TEAEs, SAEs and TEAEs leading to discontinuation of study drug can be identified from this summary.

#### 6. **Serious Adverse Events (Including Deaths) and TEAEs Leading to Study Drug Discontinuation**

All serious adverse events (SAEs), deaths, and TEAEs leading to discontinuation of study drug will be listed. The number and percentage of subjects experiencing SAEs (including deaths) and TEAEs leading to discontinuation of study drug will be tabulated by SOC and PT for each prior and current treatment group.

#### 7. **Areas of safety interest**

The list of Areas of safety interest will be based on the most updated version of the risankizumab Product Safety Statistical Analysis Plan, which is consistent with the most updated risankizumab Product Safety Plan.

#### **Grouped terms**

Grouped terms will be summarized by grouped term or SMQ, including sub-SMQs and preferred term for any adverse event, adverse events leading to discontinuation, serious adverse events, moderate or severe adverse events and related adverse events. The groupings are provided in below [Table 14](#).

**Table 14. Areas of Safety Interest Listing**

ASI Grouping	Categories (ASI)	Search Criteria	Terms to Display	Include in AE Overview (Y/N)
Adjudicated CV Events	MACE	Adjudicated terms will be identified using CECAT and CETERM from the CE SDTM dataset.	
Display underlined terms defined by the following adjudicated terms:
 
 
• CV Death which includes adjudicated results of: Sudden Cardiac death, Death due to Acute MI, Death due to Heart Failure, Death due to CV Procedures, Death due to CV Hemorrhage, Death due to Other CV Causes (specify), Fatal PE, Fatal Non-Cardiac/Non-Neuro Arterial Thrombosis/Thromboembolism, Undetermined Death, Not assessable death, fatal stroke (ischemic, hemorrhagic, undetermined)
 
• Myocardial infarction which includes adjudicated results of Type 1 Myocardial Infarction, Type 2 Myocardial Infarction, Type 3 Myocardial Infarction, Type 4 Myocardial Infarction, Type 5 Myocardial Infarction
 
• Stroke: Ischemic stroke, Hemorrhagic stroke, Undetermined stroke
 
	Y
	Extended MACE	Adjudicated terms will be identified (for MACE +) using CECAT and CETERM from the CE SDTM dataset.	
Display underlined terms from MACE and underlined terms below:
 
 
• Hospitalization for Unstable Angina
 
• Coronary Revascularization Procedures
 
	N

**Table 14. Areas of Safety Interest Listing (Continued)**

ASI Grouping	Categories (ASI)	Search Criteria	Terms to Display	Include in AE Overview (Y/N)
Adjudicated CV Events (continued)	Other CV events	Adjudicated terms will be identified using CECAT and CETERM from the CE SDTM dataset.	
Display underlined terms defined by the following adjudicated terms:
 
 
• Thrombotic events which includes adjudicated results of: Stent Thrombosis, DVT, TIA, PE, Non-fatal Non-Cardiac/Non-Neurologic Arterial Thrombosis/Thromboembolism, Other Venous Thrombosis, specified (non-fatal), Carotid revascularization
 
• Cardiac arrhythmia which includes adjudicated results of: Supraventricular Arrhythmia, Ventricular Arrhythmia, Heart Block, Other Clinically Significant Arrhythmia (no evidence of ischemia)
 
• Congestive heart failure which includes adjudicated results of Heart Failure – Requiring hospitalization, Heart Failure – Urgent heart failure visit
 
• Hypertensive emergency
 
	N
Serious infections, TB, fungal and opportunistic infections (including herpes zoster)	Serious infections	Serious PTs of the SOC Infections and Infestations	PTs	Y
	TB	Tuberculosis (including Investigations) CMQ (code 80000033)	PTs	Y
	Opportunistic infections	Opportunistic infections CMQ (code 80000073)	PTs	Y
	Fungal infections	Fungal infections CMQ (code 80000063)	PTs	N
	Herpes Zoster	Herpes zoster CMQ (code 80000175)	PTs	N

**Table 14. Areas of Safety Interest Listing (Continued)**

ASI Grouping	Categories (ASI)	Search Criteria	Terms to Display	Include in AE Overview (Y/N)
Malignancies	All possible malignancies	Narrow Malignancies (SMQ 20000090)	PTs	N
	Malignant Tumours	Narrow Malignant tumours (SMQ 20000194)	PTs	Y
	Non-melanoma skin cancer (NMSC)	Broad Skin malignant tumours (SMQ 20000204) excluding terms identified by the Melanoma CMQ (code 80000119)	PTs	N
	Malignancies excluding NMSC	'Malignancies excluding NMSC' is identified by the 'Malignant Tumours' search excluding terms identified by the 'Non-melanoma skin cancer (NMSC)' search.	PTs	Y
Hypersensitivity Reaction (Hypersensitivity Serious Event only OR Anaphylactic Reaction = "Y")	Hypersensitivity	Narrow Hypersensitivity (SMQ 20000214)	PTs	Y
	Anaphylactic Reaction	Narrow Anaphylactic reaction (SMQ 20000021)	PTs	Y
Depression, Suicidal ideation and behavior (SIB)	Suicidal ideation and behavior (SIB)	Suicide/self-injury (SMQ 20000037)	PTs	N

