H1. Avascular necrosis	Asymptomatic MRI changes, non-progressive	MRI changes and symptoms responsive to rest and analgesia	MRI changes, symptoms requiring surgical intervention	Wheelchair bound; surgical repair not possible
H2. Arthralgia	Intermittent transient symptoms, no meds or relieved by OTC meds	Persistent or recurrent symptoms, resolve with meds, little effect on function	Severe symptoms despite meds impairs function	Debilitating, hospitalisation required for treatment

H. Musculoskeletal (Continued)

H3. Leg cramps	Transient, intermittent, does not interfere with function	Recurrent symptoms, minimally interferes with function or sleep, responds to meds	Persistent, prolonged interference with function or sleep, partial or no response to meds	NA
H4. Myalgia	Occasional; does not interfere with function	Frequent, requires meds (non-narcotic); minor effects on function	Major change in function/lifestyle, narcotic pain meds	Debilitating, profound weakness, requires wheelchair, unresponsive to meds
I. Neuropsychiatric				
11. Anxiety or depression (mood alteration)	Symptomatic, does not interfere with function, no meds	Frequent symptoms, responds to meds; interferes with ADL at times	Persistent, prolonged symptoms, partial or no response to meds, limits daily function	Suicidal ideation or danger to self
12. Cerebrovascular ischaemia	NA	Single transient ischaemic event, responsive to treatment	Recurrent transient ischaemic events	Cerebrovascular vascular accident with permanent disability
13. Cognitive disturbance	Subjective symptoms, transient, intermittent, not interfering with function	Objective symptoms, persisting, interferes with daily function occasionally	Persistent, or worsening objective symptoms; interferes with routine daily routine	Debilitating/disabling and permanent; toxic psychosis
14. Depressed consciousness (somnolence)	Observed, transient, intermittent, not interfering with function	Somnolence or sedation, interfering with function	Persistent, progressive, obtundation, stupor	Coma
15. Inability to concentrate	Subjective symptoms, does not interfere with function	Objective findings, interferes with function	Persistent, prolonged objective findings or organic cause	NA

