## 11. Listing of Adverse Events

The following additional summaries of AEs will be prepared.

- Listing of Subjects with TEAE of Area of Safety Interests
- Listing of Subjects with Pretreatment Serious Adverse Events
- Listing of Subjects with Treatment-Emergent Serious Adverse Events
- Listing of all adverse events that led to discontinuation of study drug

- Listing of all deaths

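### SAP Table 14 has a safety area whose label names depression, but its only search is for suicide and self-injury

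*SAP*

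**What the plan says.** SAP section 11.2.1, item 7, says that the areas of safety interest are based on the latest version of a product-level safety SAP. The paragraph on grouped terms then sets the output: "Grouped terms will be summarized by grouped term or SMQ, including sub-SMQs and preferred term for any adverse event", and likewise for discontinuations, serious events, moderate or severe events and related events. For the content of the groups it points to Table 14: "The groupings are provided in below" that table.

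Table 14 has one column for the grouping and another for the categories within it, followed by the search, the terms to display and a Y/N flag for the AE overview. One grouping is labelled "Depression, Suicidal ideation and behavior (SIB". Its only category is SIB, its only search is "Suicide/self-injury (SMQ 20000037", preferred terms are displayed, and the overview flag is N. The next row is Hepatic Events.

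Item 11 of the same section plans a "Listing of Subjects with TEAE of Area of Safety Interests".

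**The concern.** The grouping label names two things and the search covers one. Someone programming from this SAP has no depression search to run, so the area would be filled with suicide and self-injury terms only. If the output carries the grouping label, a reader would reasonably take the count to include depression.

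Safety and tolerability are the primary objective in both documents (section 4.1 of each). The purpose of Table 14 is to give a per-subject count across related preferred terms. Without a depression search, depressive events are counted only under single preferred terms or within a whole system organ class, and the intermediate level that the label implies is missing.

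**Working it through.** No plan figure is involved, so there is nothing to recompute. The check matches what each label names to what each search covers, and then looks for a depression search elsewhere.

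1. **Depression/SIB grouping (Table 14).** Two components are named. SIB has a category and a search; depression has neither. Match: 1 of 2.

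2. **Infections grouping (Table 14), as a comparator.** Its label is "Serious infections, TB, fungal and opportunistic infections (including herpes zoster". Five components are named: serious infections, TB, fungal infections, opportunistic infections and herpes zoster. Each has its own row and search. Match: 5 of 5.

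3. **Hepatic Events (Table 14).** One category needs five standardised queries, and all five are written in its cell. The table therefore does list several searches where several are meant, and the single search for depression/SIB cannot be put down to a shorthand used throughout.

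4. **Elsewhere in the documents.** The only special-interest event that the protocol names is hepatic injury (sections 6.1.1.3 and 8.1.6.2.1). Neither document contains a depression query or a list of depression terms.

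5. **Can depression without suicidality be recorded here?** Yes. The toxicity criteria in protocol Appendix S have a row "Anxiety or depression (mood alteration". Grades 1 to 3 describe increasing symptoms, response to medication and effect on function, with no suicidality. Only grade 4 reads "Suicidal ideation or danger to self". Depressive events at grades 1 to 3 are the ones a suicide/self-injury search would be expected to miss.

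6. **Which outputs are affected?** Two: the grouped-term summary and the listing by area of safety interest. The AE overview is not, because the row is flagged N.

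7. **Where do these events still appear?** In the tables by system organ class and preferred term, by maximum severity, by maximum relationship and by descending frequency of preferred term (section 11.2.1, items 2 to 5). If serious or leading to discontinuation, they are also tabulated and listed (items 6 and 11).

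**The case against.** There are four arguments on the other side.

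- **The list is governed by another document.** The product-level safety SAP is not supplied. It may hold a depression search, or it may have dropped depression on purpose. This stands as a limit: the finding concerns the SAP text, and the final outputs could differ. It does not remove the need for an edit. If that plan has a depression search, Table 14 is incomplete; if it has none, the label is too wide.

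- **The category column defines the area.** The search and the overview flag belong to the category, and the SIB category matches its search. The SAP does not say that outputs will be titled by the grouping label. This stands in part: the printed line may read SIB, in which case the fault lies in the heading alone. The label would still promise something that the plan does not count.

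- **The events are reported anyway.** This is true for the tables and listings named above. A reader might infer that depressive events would go uncounted, or that a signal would be hidden. The documents do not support that. Each subject is counted once per preferred term and once per system organ class. Only the count at the level of a depression group is absent.

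- **Nothing in the protocol makes depression a priority.** The benefit-risk section (3.4) discusses hypersensitivity, infection, malignancy, cardiovascular events and anti-drug antibodies, not depression, and there is no control arm. This supports a low ranking. But the SAP itself put the word in the label.

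**Conclusion.** The mismatch is present on the face of Table 14, and it is minor. As the SAP is written, depressive treatment-emergent events without suicidality fall outside the grouped summary and the listing for the area that names depression. All other AE reporting of those events is intact.

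No size can be given. Neither document states a rate of depressive events, and enrolment of 180 is a ceiling. A reader might infer that the area would then show a count of zero; the documents give no basis for that either.

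The conclusion rests on three assumptions. First, the suicide/self-injury query does not retrieve general depressive terms; this is read from its name, because its term list is not given. Second, Table 14 is complete as it stands; a row lost at the table break cannot be wholly excluded, though nothing suggests one. Third, the programming follows Table 14 and does not take a different list from the product-level plan.

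**What to change.** Check Table 14 against the current product-level safety SAP. Then add a separate Depression category row to this grouping, with a search that the sponsor names explicitly and with preferred terms displayed. Leave the SIB row unchanged, and report the two rows separately in the grouped summary and the listing.

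If the product-level plan leaves depression out deliberately, shorten the grouping label to SIB so that it matches what is counted.

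The first option costs one table row, one query on AEs that are already coded, and one more summary line. The second costs a change of label. Neither needs new data collection.
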